## **12 SOURCE DOCUMENTS AND ACCESS TO SOURCE DATA/DOCUMENTS**

Each participating site will maintain appropriate medical and research records for this trial, in compliance with Section 4.9 of ICH E6 GCP, and regulatory and institutional requirements for the protection of confidentiality of subjects. As part of participating in a DMID-sponsored, DMID-affiliated or manufacturer-sponsored study, each site will permit authorized representatives of the sponsor(s), DMID, and regulatory agencies to examine (and when required by applicable law, to copy) clinical records for the purposes of quality assurance reviews, audits and evaluation of the study safety and progress.

Source data are all information, original records of clinical findings, observations, or other activities in a study necessary for the reconstruction and evaluation of the trial. Examples of these original documents and data records include, but are not limited to, hospital records, clinical and office charts, laboratory notes, memoranda, evaluation checklists, pharmacy dispensing records, recorded data from automated instruments, copies or transcriptions certified after verification as being accurate and complete, microfiches, photographic negatives, microfilm or magnetic media, x-rays, and subject files and records kept at the pharmacy, at the laboratories, and medico-technical departments involved in the clinical study.

## 13 QUALITY CONTROL AND QUALITY ASSURANCE

Following a written DMID-accepted site quality management plan, each participating site is responsible for conducting routine quality assurance (QA) and quality control (QC) activities to internally monitor study progress and protocol compliance. Each site principal investigator will provide direct access to all trial-related sites, source data/data collection forms, and reports for the purpose of monitoring and auditing by the sponsor, and inspection by local and regulatory authorities. Each site principal investigator will ensure all study personnel are appropriately trained and applicable documentations are maintained on site.

The SDCC will implement quality control procedures for the data entry system and generate database quality control checks. Any missing data or data anomalies will be communicated to the site(s) for clarification and resolution.

The VIDAS®3 Instruments and VIDAS® B.R.A.H.M.S Procalcitonin (PCT) have been commercialized in US. Both products used in this trial will be labeled with investigational use only (IUO) but they are manufactured with quality assured using the same standards with the commercialized products. Prior to the trial testing, the VIDAS®3 Instruments will be qualified by field service engineers (FSE) from bioMerieux to ensure that the instruments meet all the requirements. There will be routine maintenance to be performed by the testing lab to ensure that the instruments are under good condition. The instruments will also be checked annually by FSE from bioMerieux as annual maintenance. bioMerieux will provide support on any issues and anomalies during the trials through remote or on-site assistance.

VIDAS® B.R.A.H.M.S PCT testing are ensured by both calibration before the initiation of the trial testing and every 28 days during the trial. Internal controls are included in each patient sample testing run to provide validation of testing results of the specific run.

If any of the following situations identified, repeat testing should be performed:

- In the event of invalid control(s), the entire run must be repeated. Only the valid repeat result will be taken into account.
- In the event of established human error, or if the system does not give any results, repeat testing will be performed. Only the valid repeat result will be taken into account.

More details can be found in the product insert.

## **14 ETHICS/PROTECTION OF HUMAN SUBJECTS**

### **14.1 Ethical Standard**

The site principal investigator will ensure that this trial is conducted in full conformity with principles of the Belmont Report: Ethical Principles and Guidelines for the Protection of Human Subjects of Research of the National Commission for the Protection of Human Subjects of Biomedical and Behavioral Research (April 18, 1979) and codified in 45 CFR 46, 21 CFR 50 and 56, and ICH E6; 62 Federal Regulations 25691 (1997), if applicable. The site principal investigator's Institution will hold a current Federal Wide Assurance (FWA) issued by the Office of Human Research Protection (OHRP) for federally funded research.

### **14.2 Institutional Review Board**

Prior to enrollment of subjects into this trial, the approved protocol and informed consent form will be reviewed and approved by the appropriate IRB listed on its FWA.

The responsible official for the IRB will sign the IRB letter of approval of the protocol prior to the start of this trial and a copy will be provided to DMID. The IRB Federal Wide Assurance number will be provided to DMID.

Should amendments to the protocol be required, the amendments will be written by the sponsor and provided to the site principal investigator for submission to the IRB prior to implementation.

### **14.3 Informed Consent Process**

The site principal investigator will choose subjects in accordance with the eligibility criteria detailed in Section 5. Before any study procedures are performed, subjects must sign an informed consent form that complies with the requirements of 21 CFR Part 50 and 45 CFR 46 and the local IRB.

Informed consent is a process that is initiated prior to an individual agreeing to participate in a trial and continuing throughout the individual's trial participation. Before any study procedures are performed, subjects will receive a comprehensive explanation of the proposed study procedures and study interventions/products, including the nature and risks of the trial, alternate therapies, any known AEs, the investigational status of the components, and the other elements that are part of obtaining proper informed consent. Subjects will also receive a detailed explanation of the proposed use and disclosure of their protected health information. Subjects will be allowed sufficient time to consider participation in the trial, after having the nature and risks of the trial explained to them, and have the opportunity to discuss the trial with their family, friends or legally authorized representative or think about it prior to agreeing to participate.

Informed consent forms describing in detail the study interventions/products, study procedures, risks and possible benefits are given to subjects. The informed consent form must not include any exculpatory statements. Informed consent forms will be IRB-approved and subjects will be asked to read and review the appropriate document. Upon reviewing the appropriate document, the site principal investigator (or designee) will explain the research study to subjects and answer any questions that may arise. Subjects must sign the informed consent form, and written documentation of the informed consent process is required prior to starting any study procedures/interventions being done specifically for the trial, including administering study product.

DMID will provide the site principal investigator, in writing, any new information that significantly impacts the subjects' risk of receiving the investigational product. This new information will be communicated by the site principal investigator to subjects who consent to participate in the trial in accordance with IRB requirements. The informed consent document will be updated and subjects will be re-consented per IRB requirements, if necessary.

Study personnel may employ recruitment efforts prior to obtaining study consent if a patient-specific screening consent is on record or if the IRB has agreed that chart review is allowed without a fully executed screening consent. In cases where there is not a patient-specific screening consent on record, site clinical staff may pre-screen via chart review and refer potential subjects to the research staff. Research staff would obtain written consent per the standard informed consent process before conducting protocol-specific screening activities.

Subjects will be given a copy of all informed consent forms that they sign. By signing the informed consent form, subjects agree to complete all evaluations required by the trial, unless the subject withdraws voluntarily, or is withdrawn or terminated from the trial for any reason.

The rights and welfare of subjects will be protected by emphasizing to subjects that the quality of their medical care will not be adversely affected if they decline to participate in or withdraw from this trial.

#### **14.3.1 Informed Consent/Assent Process (in Case of a Minor or others unable to consent for themselves)**

N/A

#### **14.4 Exclusion of Women, Minorities, and Children (Special Populations)**

This study is focused on individuals aged 18 or greater of all racial, ethnic, and gender/sex categories.

## 14.5 Subject Confidentiality

Subjects will have code numbers and will not be identified by name. Subject confidentiality is strictly held in trust by the participating investigators, their staff, and the sponsor(s) and their agents.

The study protocol, documentation, data, and all other information generated will be held in strict confidence. No information concerning the study or the data will be released to any unauthorized third party without prior written approval of the sponsor.

All information provided by the Sponsor and all data and information generated by the participating site as part of the trial (other than a subject's medical records) will be kept confidential by the site principal investigator and other study personnel to the extent permitted by law. This information and data will not be used by the site principal investigator or other study personnel for any purpose other than conducting the trial. These restrictions do not apply to: (1) information which becomes publicly available through no fault of the site principal investigator or other study personnel; (2) information which is necessary to disclose in confidence to an IRB solely for the evaluation of the trial (3) information which is necessary to disclose in order to provide appropriate medical care to a study subject; or (4) study results which may be published as described in Section 16.

The study monitor, applicable regulatory authorities, such as the FDA, or other authorized representatives of the sponsor may inspect all documents and records required to be maintained by the investigator, including but not limited to, medical records (office, clinic, or hospital) and pharmacy records for the subjects in this study. The clinical study site will permit access to such records.

## 14.6 Study Discontinuation

If the trial is discontinued, subjects who sign the informed consent form, and are randomized and treated will continue to be followed for safety assessments. No further study treatment will be administered.

## 14.7 Future Use of Stored Specimens

Subjects will be asked for permission to keep any samples for use in future research studies. Samples may be stored temporarily at the local site or longer term at DMID CMS central clinical storage facility. Samples may be shared with other investigators at other institutions, provided that appropriate human subject protection plans are in place and DMID has been consulted and approved of the use. The samples will not be sold or used directly for production of any commercial product. No human genetic tests (i.e., DNA testing) will be performed on samples, although measures of gene expression may be performed. Each sample will be encoded (labeled) only with a barcode and a unique tracking number to protect subject's confidentiality.

There are no benefits to subjects in the collection, storage and subsequent research use of specimens. Reports about future research done with subject's samples will not be kept in their health records.

Subjects may be given the option to decide if they want their samples to be used for future research or have their samples destroyed at the end of the trial. The subject's decision can be changed at any time prior to the end of the trial by notifying the study doctors or nurses in writing. However, if the subject originally consents to future use and subsequently changes his/her decision, any data from a previously collected sample may still be used for this research.

## **15 DATA HANDLING AND RECORD KEEPING**

The investigator is responsible to ensure the accuracy, completeness, legibility, and timeliness of the data reported.

Data collection forms will be derived from the eCRFs and provided by the SDCC to the sites to record and maintain data for each subject enrolled in the study. All source documents should be completed in a neat, legible manner to ensure accurate interpretation of data. Permanent ink is required to ensure clarity of reproduced copies. When making a change or correction, the original entry should be crossed out with a single line, and the change should be initialed and dated. Do not erase, overwrite, or use correction fluid or tape on the original.

Data reported in the eCRF should be consistent with the data collection form/source documents or the discrepancies should be documented.

The sponsor and/or its designee will provide guidance to investigators on making corrections to the data collection forms and eCRFs.

### **15.1 Data Management Responsibilities**

All source documents and laboratory reports must be reviewed by the clinical team and data entry staff, who will ensure that they are accurate and complete. Adverse events must be graded, assessed for severity and causality, and reviewed by the site PI or designee.

Data collection is the responsibility of the clinical trial staff at the site under the supervision of the site PI. During the study, the investigator must maintain complete and accurate documentation for the study.

Emmes will serve as the Statistical and Data Coordinating Center for this study and will be responsible for data management, quality review, analysis, and reporting of the study data.

### **15.2 Data Capture Methods**

Clinical data (including solicited events, UADEs, and concomitant medications) and clinical laboratory data will be entered into a 21 CFR Part 11-compliant Internet Data Entry System (IDES) provided by Emmes. The data system includes password protection and internal quality checks, such as automatic range checks, to identify data that appear inconsistent, incomplete, or inaccurate. Clinical data will be entered directly from the source documents.

### **15.3 Types of Data**

Data for this study will include clinical, laboratory, safety, and outcome measures.

## 15.4 Timing/Reports

A final report will be prepared following the availability of all the safety and efficacy data. Interim safety reports may be generated for the DSMB safety review.

After full analysis and final reporting is complete, and upon request and DMID approval, the SDCC will provide the participating sites with a summary of results by treatment group and/or subject treatment assignments. In this regard, the participating sites requesting such information to share with study subjects must do so in compliance with their respective IRB guidelines.

## 15.5 Study Records Retention

Records and documents pertaining to the conduct of this study, including data collection forms, source documents, consent forms, laboratory test results, and medication inventory records shall be retained until at least 2 years after the last approval of a marketing application in an ICH region or at least 2 years have elapsed since the formal discontinuation of clinical development of the investigational product. The site must contact DMID for authorization prior to the destruction of any study records. Informed consent forms for future use will be maintained as long as the sample exists.

## 15.6 Protocol Deviations

A protocol deviation is any noncompliance with the clinical trial protocol, Good Clinical Practice (GCP), or Manual of Procedures requirements. The noncompliance may be either on the part of the subject, the investigator, or the study site staff. As a result of deviations, corrective actions are to be developed by the site and implemented promptly.

These practices are consistent with ICH E6:

4.5 Compliance with Protocol, sections 4.5.1, 4.5.2, and 4.5.3

5.1 Quality Assurance and Quality Control, section 5.1.1

5.20 Noncompliance, sections 5.20.1, and 5.20.2.

It is the responsibility of the site to use continuous vigilance to identify and report deviations within 5 working days of identification of the protocol deviation, or within 5 working days of the scheduled protocol-required activity. All deviations must be promptly reported to DMID, via the Emmes IDES

All deviations from the protocol must be addressed in study subject source documents. A completed copy of the DMID Protocol Deviation Form (IDES form) must be maintained in the regulatory file, as well as in the subject's source document. Protocol deviations must be sent to

the local IRB/IEC per their guidelines. The site PI/study staff is responsible for knowing and adhering to their IRB/IEC requirements.

## 16 PUBLICATION POLICY

This study will be conducted in accordance with the following publication and data sharing policies and regulations:

National Institutes of Health (NIH) Public Access Policy, which ensures that the public has access to the published results of NIH funded research. It requires scientists to submit final peer-reviewed journal manuscripts that arise from NIH funds to the digital archive PubMed Central upon acceptance for publication.

This study will comply with the NIH Data Sharing Policy and Policy on the Dissemination of NIH-Funded Clinical Trial Information and the Clinical Trials Registration and Results Information Submission rule. As such, this trial will be registered at [ClinicalTrials.gov](http://ClinicalTrials.gov), and results information from this trial will be submitted to [ClinicalTrials.gov](http://ClinicalTrials.gov). Following completion of the study, the investigator is expected to publish the results of this research in a scientific journal.

### **Appendix A: Schedule of Events**

	Visit #1 Screening, Enrollment, & Randomization	Visit #2*	Visit #3	Visit #4*	Visit #5*	Early Termination Visits	Visit 5N (non- randomized Subjects)
Visit Number	01	02	03	04	05		5N 
Visit Day 	Day 1	Day 3 +1	Day 5 +3	Day 11 +3	Day 28 ±2		Day 28+7
Obtain Informed Consent	X						
Assessment of Sociodemographic Data	X						
Randomization 	X						
Dispense study drug 	X						
Collection of study product bottle			X			X 	
Review inclusion/exclusion criteria	X						
Assessment of medication compliance		X	X			X 	
Assessment of Solicited AEs		X	X	X		X	
Assessment of UADEs		X	X	X	X	X	
Medical history 	X		X	X	X	X	X 
Physical exam 	X		X			X 	
Vital signs 	X		X			X 	
Assessment of LRTI signs and symptoms	X	X	X	X	X	X	
Concomitant medications 	X	X	X	X	X	X	X 
Distribute Memory Aid and Study-Related Materials	X						
Review Memory Aid		X	X	X		X 	
Serum or Plasma PCT	X		X			X 	
Nasopharyngeal Swab	X						
PAXgene Blood RNA (for future use, if consented)	X						

Footnotes:

- \* Phone call assessment.
- 1. There will be a window around each of the scheduled follow-up assessments to allow for subject and staff flexibility.
- 2. Subjects with a PCT ≤0.25 ng/mL who satisfy the inclusion criteria with no exclusion criteria will be enrolled and randomized.

3. Study drug will be azithromycin or placebo.
4. Medical history will include: drug allergies, co-morbidities.
5. Physical exam will include: assessment of general appearance, a focused HEENT, neck, cardiopulmonary, and abdominal examination
6. Vital signs: temperature, pulse, blood pressure, respiratory rate, and pulse oximetry will be recorded. Care related exam findings and vital signs may be used.
7. These will be performed if indicated as part of the next regularly scheduled visit.
8. All data will be collected from a medical record review only. The subject will not be contacted.
9. All concomitant medications will be documented at Visit #1. Any symptomatic treatment received on the day of/during the enrollment visit will not be recorded unless it is a non-study systemic antibiotic.

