### **7.2 Enrollment/Baseline- Visit 1 (Day 1)**

At the Enrollment Visit, study staff will obtain written informed consent from the subject for the primary study and for future use of samples and data. Declination to participate in collection of future use samples will not affect participation in the primary study. After the subject has had the opportunity to ask questions and has signed the informed consent document, the following activities will be performed:

- Eligibility criteria for enrollment will be reviewed;
- An assessment of LRTI signs and symptoms will be made
- Blood samples will be obtained and used for PCT measurement and future use (if consented).

Additional information will be obtained from the subject as follows:

- A complete medical history and sociodemographic data will be obtained by direct interview of the subject and medical record review
- A physical examination will be performed to determine general appearance and focused HEENT, neck, cardiopulmonary, and abdominal examinations; vital signs, including

temperature, blood pressure, pulse rate, respiratory rate, and pulse oximetry (obtained clinically).

*\* Note: physical examinations may be performed by physicians, advanced practice nurses, physician assistants, or nurses obtained either by study investigators or as part of clinical care.*

- Concomitant medications taken in the last 30 days will be recorded based on subject report or medical record review (see section 6.6. for details)
- A nasopharyngeal swab specimen will be collected for respiratory viral testing and banking.

The PCT value is expected to be available to the investigator within 2 hours of the blood draw. The study team will not report PCT results to the subject or the provider. Once the subject's PCT value is available, subjects with a PCT > 0.25 ng/mL will not be randomized. Providers will be notified that the patient will not be randomized and therefore, the treating provider should make treatment decisions.

Subjects with PCT ≤ 0.25 ng/mL will be randomized 1:1 to receive oral azithromycin or placebo and the following procedures will be performed:

- Study product will be dispensed and study staff will review the study product with the subject and review the study product storage and dosing instructions. Preferably, the study staff will witness the subject take the first dose of study product, which will be recorded on the memory aid.

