Solicited event assessments will include an assessment of solicited events occurring from the time of enrollment through Visit 4 (Day 11+3 days). All subjects will be instructed to complete a subject memory aid from the time of enrollment through Visit 4 (Day 11+3 days). Subject memory aids will be reviewed with the subject for any discrepancies or missing data and data will be recorded by study coordinators.

*\* Note: physical examinations may be performed by physicians, advanced practice nurses, physician assistants, or nurses.*

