#### **9.2.2 Solicited Adverse Events**

Solicited adverse events are common and known to occur following administration of the study product. Solicited adverse events will be recorded according to the study timeline. Solicited adverse events will be used to determine DOOR assignment as summarized in Table 3, Section 3.

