3.3. Study Definitions and Derived Variables

3.3.1. Timepoints

Day 5 Visit (D5V) represents Visit 3 which can occur any time from Day 5 to Day 8.

Day 11 Visit (D11V) represents Visit 4 which can occur any time from Day 11 to Day 14.

Day 28 Visit (D28V) represents Visit 5 which can occur any time from Day 26 to Day 30.

Day 1 is defined as the date of dose 1 for subjects treated with study product. For subjects not treated with study product, Day 1 will use their randomization date. The enrollment date will be used to define Day 1 for non-randomized subjects with PCT > 0.25 ng/mL. There is no Day 0 for this study, and the day preceding Day 1 will be reported as Day -1.

Study Day is defined relative to Day 1. If a visit did not occur, then study day will be imputed as its planned study day. Moreover, if a visit occurs out of the protocol defined window, then that visit will be treated as missing and its study day imputed as the planned study day in the Intention-to-Treat (ITT) analysis. Note that planned study day is 5 for D5V, 11 for D11V, and 28 for D28V.

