6.5.3. Most Severe Solicited Event for DOOR

If a subject had severity grades (0 to 3) recorded for every solicited event (abdominal pain, vomiting, diarrhea, allergic reaction, and candidiasis) from Study day 1 to D5V Study day, inclusive, then the most severe solicited event at D5V, a component of DOOR, will be the maximum severity grade taken across all solicited events from Study Day 1 to D5V Study Day.

If a subject had any solicited event of severity grade 3 from Day 1 to D5V Study Day, then the most severe solicited event at D5V will be grade 3, regardless of the presence of missing data during that period. Otherwise, if the subject has missing data for the severity grade of any solicited event from Day 1 to D5V study day, then most severe solicited event at D5V will be missing.

If a subject had severity grades (0 to 3) recorded for every solicited event (abdominal pain, vomiting, diarrhea, allergic reaction, and candidiasis) from study day 1 to study day 11, inclusive, then the most severe solicited event at D11V, a component of DOOR at D11V, will be the maximum severity grade taken across all solicited events from study day 1 to study day 11.

If a subject had any solicited event of severity grade 3 from Day 1 to study day 11 study day, then the most severe solicited event at study day 11 will be grade 3, regardless of the presence of missing data during that period. Otherwise, if a subject has missing data for the severity grade of any solicited event from Day 1 to study day 11 study day, then most severe solicited event at D11V will be missing.

A similar approach as described above will be used to determine the most severe solicited event at D28V by considering all solicited events reported post dose 1.

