9.3.1. Solicited Events and Symptoms

Solicited events will be captured from Day 1 until Day 11. For those with multiple solicited events, the ordinal response table will be based upon the most severe solicited event.

Solicited events were recorded for trial Days 1-11, or until study completion or termination, as the maximum severity for each day. Target solicited events include abdominal pain, vomiting, diarrhea, allergic reaction, and candidiasis.

The proportion of subjects in each treatment group experiencing each solicited event will be tabulated by treatment group (Table 65). The proportion of subjects in each treatment group experiencing each solicited event will be tabulated by treatment group and severity (Table 66). The proportion of subjects in each treatment group experiencing each solicited event will also be tabulated by day and severity level (Table 67 and Table 69). Finally, solicited events will be analyzed by taking the most severe response over the follow-up period, dichotomizing into a binary variable (mild or greater, moderate or greater, severe) (Table 68). Proportions for these derived binary variables will be reported along with 95% CIs using the Wilson method. Comparisons of proportions by treatment groups will be given as risk differences (with 95% CIs from the Miettinen–Nurminen method) and p-values from Fisher’s Exact Test.

The maximum severity occurrence of each solicited event (proportion of subjects for each severity level) will be plotted for each solicited adverse event (Figure 27). Solicited events by subject will also be presented (Listing 9).

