16.2.6 Adverse Events

Listing 9: 16.2.6: Solicited Events

[Implementation Note: This listing is not color-coded. This listing includes baseline assessments in addition to post-treatment assessments. In the CSR, Subject ID should be USUBJID (not PATID) for purposes of de-identification. Sort order: Subject ID, Dose Number, Post Dose Day, Symptom.]

Treatment Group	Subject ID	Study Day	Abdominal Pain	Vomiting	Diarrhea	Allergic Reaction	Candidiasis
Placebo	SST.XXXX	1	MILD	MILD	NONE	SEVERE	NONE

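### No pre-dose solicited-event grade is scheduled and no new-or-worsened rule exists, so events present at enrollment that persist count in both arms and dilute the harm comparison and, slightly, DOOR

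*Protocol*

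**What the plan says.** **Schedule.** In Protocol Appendix A, and in its copy in SAP Table 4, the row "Assessment of Solicited AEs" is marked at Visits 2, 3, 4 and Early Termination and is empty at Visit 1. Protocol 7.2 lists for Visit 1 that "An assessment of LRTI signs and symptoms will be made", together with history, examination and samples. It does not list a solicited-event grade. Staff hand out the memory aid and train the subject to use it.

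**Collection.** Protocol 8.1 describes "an assessment of solicited events occurring from the time of enrollment through Visit 4". SAP 9.3.1 says "Solicited events were recorded for trial Days 1-11, or until study completion or termination, as the maximum severity for each day". SAP 3.3.1 says "Day 1 is defined as the date of dose 1 for subjects treated with study product".

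**Counting.** Under SAP 6.5.3 the most severe event at D5V "will be the maximum severity grade taken across all solicited events from Study Day 1 to D5V Study Day". No rule compares this grade with enrollment. By SAP 6.5.4 it separates ordinal levels 1 to 4; levels 5 to 8 ignore it. The same events feed the arm comparisons in SAP 8.2.9, 8.3.4 and 9.3.1.

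**A conflicting statement.** The note to Listing 9 (SAP Appendix 3, 16.2.6) says "This listing includes baseline assessments in addition to post-treatment assessments". The schedule provides no such assessment, and no planned analysis uses one.

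**The concern.** Protocol 9.2.2 describes the target events this way: "Solicited adverse events are common and known to occur following administration of the study product". Vomiting, diarrhea and abdominal pain can also come with the presenting illness or with earlier treatment. Protocol 5.1 admits subjects up to 28 days after symptom onset. Protocol 5.2 excludes azithromycin use in the past two weeks but other systemic antibiotics only in the previous 24 hours, so a subject may enroll days after a different antibiotic with diarrhea or candidiasis already present.

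If such an event persists after enrollment, it counts. An improved subject then moves from ordinal level 1 to level 2, 3 or 4 whichever arm he or she is in. Protocol 9.1 makes solicited events the only azithromycin adverse-event data collected, and Protocol 2.3.2 names fewer antibiotic adverse events as a benefit of withholding treatment. A background common to both arms makes a true azithromycin excess harder to see in the data meant to show it.

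LRTI symptoms are handled differently: SAP 6.5.1 takes a Visit 1 severity as baseline. Solicited events have no counterpart.

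**Working it through.** The documents give no expected rate, power or baseline prevalence for solicited events, so there is no planned figure to reproduce. The calculation below is an illustration.

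**From the documents:** 1:1 allocation; 280 per arm in ATP-5 (SAP 6.6), the population used in SAP 8.2.9; about 337 per arm randomized (Protocol 5).

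**Assumed:** new-event risk p of 20% on azithromycin and 12% on placebo; a fraction b of subjects in each arm enroll with an event that persists and is recorded; new events occur independently of it.

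**Formulas.** Observed risk r = b + (1−b)p. The observed difference is (1−b)(0.20 − 0.12), so it shrinks by exactly (1−b). SE = √{[r_A(1−r_A) + r_P(1−r_P)]/n}. Power ≈ Φ(difference/SE − 1.96).

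**Worked case, b = 10%, n = 280.** r_A = 0.10 + 0.90×0.20 = 0.280. r_P = 0.10 + 0.90×0.12 = 0.208. The difference is 0.072. SE = √[(0.2016 + 0.1647)/280] = 0.0362. Power = Φ(1.99 − 1.96) = 51%.

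| b | Observed risks, A vs P | Difference | Power, n = 280, as written | Power, n = 280, new events only |
|---|---|---|---|---|
| 0 | 20.0% vs 12.0% | 8.0 points | 74% | 74% |
| 2% | 21.6% vs 13.8% | 7.8 | 69% | 73% |
| 5% | 24.0% vs 16.4% | 7.6 | 61% | 71% |
| 10% | 28.0% vs 20.8% | 7.2 | 51% | 68% |
| 20% | 36.0% vs 29.6% | 6.4 | 37% | 62% |

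The last column uses risks (1−b)p. The difference is the same as in the as-written count, and the gain comes from lower variance. Counting worsened events as well can restore some of the difference, with the b = 0 value (74%) as the ceiling. At 337 per arm the as-written figures are 69%, 59% and 43% for b = 5%, 10% and 20%, against 81% at b = 0.

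SAP 8.2.9 plans Fisher's exact test, which is more conservative. At 280 per arm it lowers the as-written figures for b = 5%, 10% and 20% by about 3 to 5 points.

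**DOOR at Day 5.** Further assumptions: 57.6% improved in both arms; new-event risks of 10% on placebo and 20% on azithromycin; event grades split 60/30/10; no medically attended events or deaths; 0 versus 5 antibiotic days. At b = 0 the probabilities of levels 1 to 5 are 0.518, 0.035, 0.017, 0.006, 0.424 on placebo and 0.461, 0.069, 0.035, 0.012, 0.424 on azithromycin. Then P(placebo better) = 0.306 and P(tie) = 0.422. On the ordinal outcome alone, the DOOR probability is 0.306 + 0.422/2 = 0.517. With every tie broken by antibiotic days it is 0.306 + 0.422 = 0.727 (unrounded inputs). At b = 30% the two values become 0.512 and 0.672.

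**The case against.** **Were events graded before the first dose or not?** A reader might infer from the blank cell that they were not. The documents do not settle this. Listing 9 refers to baseline assessments, and Protocol 8.1 starts collection at enrollment. What stands is that no such grade is scheduled, that none is used, and that the two statements conflict. Because Day 1 is the date of dose 1 and only a daily maximum is kept, the Day 1 record cannot separate hours before the dose from hours after it.

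**Are these scored as drug events?** A reader might infer that too. They are not: SAP 6.5.3 and 6.5.4 attach no causality and compare randomized arms. Background is expected to be equal, so the result does not lean toward either arm. DOOR ranks what the subject experienced, and counting every event is a defensible definition of that.

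**Do the existing definitions already filter background?** In part. The rash grades require a new finding, and diarrhea is graded relative to normal stools, which may remove habitual loose stools but not an illness that began before enrollment. Abdominal pain, vomiting and candidiasis carry no such wording. Mild background does not enter the moderate-or-greater and severe thresholds. Safety Tables 65 to 68 refer to severity post dosing, but a persisting event is still reported after dosing. Tables 67 and 68 show grades day by day, so early background is partly visible.

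**Is the size known?** No. At b = 2% the loss is 5 points, from 74% to 69%, and the 37% figure needs b = 20%. No power is claimed for these comparisons.

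**Conclusion.** The point holds as dilution of unknown size. Without a scheduled pre-dose grade or a new-or-worsened rule, persisting events from before enrollment enter the solicited-event comparisons and ordinal levels 1 to 4 in both arms. The risk difference shrinks by (1−b), and power falls faster because the variance also rises. DOOR moves slightly toward 0.50 and stays well above it with the tie-breaker under the assumptions shown.

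A reader might go further and infer that the trial's main conclusion is at risk. The documents do not support that: clinical improvement at Day 5 uses no solicited-event data, so only secondary, exploratory and safety analyses are affected. The power figures rest wholly on assumed event rates, an assumed b, full persistence of background events, and a normal approximation in place of the planned Fisher test. This is a worthwhile, low-cost improvement rather than a defect that undermines the trial.

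**What to change.** 1. Add a pre-dose solicited-event grade at Visit 1, on the existing form, in Protocol Appendix A, Protocol 7.2 and SAP Table 4. State whether the baseline assessments named in Listing 9 exist, and reconcile that note with the schedule.
2. In SAP 8.2.9, 8.3.4 and 9.3.1, report events that are new or of higher grade than at Visit 1 beside the all-events count.
3. For DOOR (SAP 6.5.3), keep the current definition and add the new-or-worsened version as a sensitivity analysis. Treat a missing Visit 1 grade as 0. Otherwise the rule would add a required value and create further missing OCO and DOOR values.
4. If no pre-dose grade can be obtained, run the sensitivity analysis counting only events worse than the recorded Day 1 grade, and state the limitation: an event that truly began after the dose on Day 1 would be discounted too. The past tense in SAP 9.3.1 and the screening periods ending March 2020 in SAP Table 10 suggest that collection may be over, though this is an inference. SAP 8.4.2 already lists the Day 1 maximum grade as an imputation variable.

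The cost is five graded questions at an in-person visit that already takes place, a few minutes of interview time, and one derived variable. The fallback in step 4 needs programming only.
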